## I. Hypotheses and Specific Aims

### **R00 Phase: Proof-of-Concept Study of the Narrative Intervention**

**Specific Aim 1, Outcome Measures:** Compare the effects of the narrative intervention to usual care on the primary outcome of patients' perceptions of quality of communication and on the secondary outcomes of patients' physical function, anxiety, depression, fatigue, sleep, ability to participate in social roles/activities, pain interference and intensity, and psychosocial illness experience.

**Specific Aim 2, Process Measures:** Establish acceptability, feasibility, and usability of the narrative intervention through identification of barriers and facilitators of the narrative intervention from the perspectives of the key stakeholders—patients with serious illness and acute-care bedside nurses—through patient and nurse exit interviews; field analysis of EHR interface use and end-user usability surveys of the nurses.

#### **Impact**

The *expected outcome of the R00* phase will be completion of the preliminary testing of the narrative intervention. The immediate next steps in my program of research would be an efficacy trial (Phase III) of the narrative intervention. This proposal will continue to build my program of research working with patients with serious illness and providing the foundation for future R01 applications testing and tailoring person-centered communication interventions to improve quality of life for palliative care patients. The proposed study aligns clearly with NINR's strategic focus on palliative care science, addressing disparities, and evaluating patient-centered interventions to optimize QoL.

## II. Background and Significance

Health care advances have extended the lifespan and cured many diseases; however, advanced health care treatments are sometimes discordant with patient preferences, values, and beliefs, which can lead to insufficient symptom control, difficult patient-provider interactions, and poor psychosocial and spiritual support. Further, poor patient-provider communication contributes to continued unwanted care.

A comprehensive palliative care approach improves communication, leading to better quality of life (QoL) for patients, yet discordant care continues in part because of knowledge gaps about patient psychological, social, and spiritual needs. Person-centered narrative interventions can fill these knowledge gaps, yielding an increased understanding of patient psychological, social, and spiritual needs, which will help providers develop tailored palliative care interventions. The use of storytelling (narrative) is an effective way for patient's to communicate their cultural values and beliefs, however, in the healthcare system, patients do not always have the opportunity to share these values/beliefs with providers.

In the health care setting, the electronic health record (EHR) is one of the primary modes of communication about patients, but most of this information is provider-centered. There is a need to integrate more of the patient as person into the patient's health record. Incorporating a patient's narrative into the EHR provides an opportunity to communicate patient's cultural values/beliefs to the healthcare team and has the potential to improve patient-nurse communication. However, there is limited research on effective integration of a patient's narrative into the EHR. This proposal investigates an innovative way to integrate patient values/beliefs into the EHR through a narrative intervention. The *central hypothesis* of this proposal is that implementing a person-centered narrative intervention with hospitalized patients will result in improved patient-nurse communication and improve patient's psychological and social well-being.

Instructions – How to complete the COMIRB protocol template (Social)  
CF-184, Effective 4-26-2010

## Significance

### Importance of Person-Centered Narrative Interventions that Incorporate Cultural Values and Beliefs

Person-centered care includes shared decision-making, holistic patient care with respect for patient's preferences and goals, attention to non-medical aspects of care, communication, knowing the patient as person, and understanding culture, which influences health behaviors and the meaning of illness. Communication appears to be one critical element of person-centered care. Story theory can be applied to person-centered care because of its foundation in "meaning making"24,pg.205 built on intentional dialogue, creating ease, and connecting with self-in-relation. Using the foundation of story theory, patient narratives about illness experiences offer providers a view into patients' cultural attitudes about their illness and patients' psychological, social, and spiritual beliefs/values. When a nurse knows more of the patient's narrative, improved quality of communication may occur, which can create opportunities for culturally congruent care and lead to improved patient QoL. A narrative intervention implemented with patients living with serious illness can draw together the complexities and varied cultural meanings of illness experiences, which can improve QoL and decrease suffering. Patient participation in narrative interventions has been linked to reduced pain, stress, anxiety, and fatigue, and improved psychosocial and QoL outcome measures.

## Innovation

[figure not shown]
### Integration of a Person-Centered Narrative into the EHR

Some research has shared the patient's narrative with families, e.g. life review on DVD or digital storytelling uploaded to YouTube, and found positive outcomes. However, minimal research has integrated narrative interventions into the EHR in a meaningful and efficient way and tested whether the narrative intervention could improve communication between patient and nurse and impact the patient's overall well-being. There is an urgent need to investigate innovative ways to incorporate the patient's narrative into their healthcare record. In our fragmented health care systems, the lack of personhood increases suffering, thus decreasing QoL for this population. The integration of a person-centered narrative intervention into the EHR could benefit patients and nurses interacting in technology-rich environments. Since the EHR is one of the primary modes of communicating health care information about the patient, the integration of patients' narratives into the EHR has the potential 1) to improve person-centered care by incorporating patient's values/beliefs, 2) to provide opportunities to enhance patient-to-nurse communication, and 3) to positively impact patient's psychosocial and spiritual well-being.

## III. Preliminary Studies/Progress Report

### Relevance of Research to My Career Goals

I have based my research program on the ORBIT model for developing and testing behavioral intervention ( Figure 1). During my dissertation, I conducted qualitative work that provided a rich understanding of how to form a significant clinical question: How can narrative interventions be used to improve communication among patients with serious illness and their providers? Using this question, my K99 study assisted in refining and defining the narrative intervention (Phase 1). For this R00 proposal, preliminary testing of the narrative intervention will be studied (Phase II).

## Preliminary Data

**Dissertation.** By using the ORBIT model to build a program of behavioral interventional research, my dissertation research provided insight about "identifying attitudes, norms, and values that could affect an intervention's acceptability and feasibility."33, p. 976 Using Riessman's narrative methods for human sciences, I completed an exploratory descriptive study using a narrative analysis methodology that explored the phenomenon of psycho-social-spiritual healing among African American elders with serious illness. Second,

I examined the NIH Clinical Center Palliative Care and Pain Service's psycho-social-spiritual healing measure as a culturally appropriate instrument for African American elders with serious illness. Cognitive interview methodology, verbal probing, and think-aloud techniques were used to gain expert input from African American elders with serious illness regarding the instrument. This, coupled with my years of palliative care nursing practice, began a process of observing how narratives could provide a person-centered palliative care intervention. In addition, my in-depth study of narrative methodologies helped reveal the possible utility of narratives as an intervention to improve psychological, social, and spiritual suffering for patient with serious illness.

**K99 Phase: Define Narrative Intervention (Phase I ORBIT Model).** The outcome of the K99 phase helped define the narrative intervention and test the preliminary feasibility and acceptability of the intervention from two key stakeholders: the hospitalized patient with serious illness (n=20) and the acute care bedside nurse (n=18). The 20 patient participants and the 18 nurse participants found participation in the study easy and beneficial. Eighteen of 20 patient participants discussed their narrative with others, including family (n=12); friends (n=2), and health care team members (n=15). Healthcare team members included nurses (n=10); physicians (n=3), and nursing aides (n=2). Eighteen of 20 patient participants confirmed that they would be willing to participate in a similar type of intervention in the future. All eighteen nurse participants described having positive experiences. Nurses described the intervention as “eye opening” giving them a “different perspective about what their patients are going through emotionally and physically” and allowed them to “connect” to their patient.

## **IV. Research Methods**

### **Proposed Study**

#### **R00 Phase: Preliminary Testing of Narrative Intervention (Phase II ORBIT Model)**

For Aim 1, this study will test: 1) the effects on quality of communication between patient and nurse, as measured by the patient, 2) the effect of the intervention on patient's overall biopsychosocial and spiritual well-being, as measured by the PROMIS 29 profile, and 3) the effects on patient's psychosocial illness impact, as measured by the PROMIS psychosocial illness impact. For Aim 2, this study will test acceptability, feasibility, and usability of the narrative intervention from the perspectives of the key stakeholders—patients with serious illness and acute-care bedside nurses via 1) patient and nurse exit interviews, 2) field analysis of EHR interface use, and 3) end-user usability surveys of the nurses. This study builds on knowledge from the K99 study and will continue the optimization of the biobehavioral narrative intervention by providing the necessary preliminary data required to submit an independent R01 grant, an efficacy trial (Phase III Orbit Model).

### **A. Outcome Measure(s)**

#### **Aim1: Outcome Measures:**

**Primary outcome—Quality of Communication (QOC).** The QOC survey assesses patients' perceptions of the quality of communication with nurses. The QOC was initially developed from qualitative interviews and focus groups with diverse set of patients, families and providers. The QOC has 19 items, with scores ranging from 0 (worst) to 10 (best). Internal consistency reliability and construct validity of the QOC has been established across several illness groups, and the QOC survey's responsiveness to communication interventions has been demonstrated by changes in pre- and post-intervention scores.

**Secondary Outcomes. PROMIS measures.** This study will use the two PROMIS measures for patient reported outcomes: 1) PROMIS- 29 profile v2.0 form (29 items), which assesses physiological, social, and psychological outcomes. These biopsychosocial domains include physical function, anxiety, depression, fatigue, sleep, ability to participate in social roles/activities, pain interference and intensity and 2) PROMIS psychosocial illness impact items assesses negative and positive aspects of the illness experience. The PROMIS positive item bank measure (8 items) assesses positive psychosocial outcomes of illness. The positive psychosocial illness impact refers to outcomes that can occur as a result of confrontation with one's mortality, such as greater life appreciation, interpersonal relationships, and personal resources. The PROMIS

negative item bank measure (8 items) assesses the direct negative psychosocial effect of illness, distinct from general emotional distress. The positive or negative items do not, however, seek to capture the impact of illness on physical or functional domains. All PROMIS measures have established reliability and validity.

**Table 1. Outcome Data**

Participant	Time 1: Baseline	Time 2: 24-48 hours post baseline/narrative upload	Time 3: 24-48 hrs after Time 2	1- week Post Upload
Patient	1. Quality of Communication(19)* 2. PROMIS-29 Profile:v2.1(29)* 3. PROMIS Psychosocial Illness Impact a)Positive affect (8)* b) Negative affect (8)* 4. Demographics	1. Quality of communication(19)* 2. PROMIS-29 Profile:v2.1 (29)* 3. PROMIS Psychosocial Illness Impact a)Positive affect (8)* b) Negative affect (8)*	1. Quality of communication(19)* 2. PROMIS-29 Profile:v2.1 (29)* 3. PROMIS Psychosocial Illness Impact a)Positive affect (8)* b) Negative affect (8)*	
Nurse				System Usability Scale (10)*
Pt/Nurse				Exit Interviews

\*(n)= number of items in outcome measure

## B. Description of Population to be Enrolled

**Setting/Sample.** This study will be conducted at University of Colorado Hospital, the same setting of the K99 study. As in the K99 study, there will be patient participants and acute care bedside nurse participants.

**Patient participants.** Patient participants (N = 80) will include those from two illness groups: heart failure and end-stage renal disease. The sample size was chosen to be consistent with pilot and usability studies.

**Patient Eligibility Criteria.** Patients will be age 18 or older, able to speak/read English, capable of giving informed consent, and be diagnosed with at least one serious illness. The operational definition of serious illness for this study will include the following: 1) New York Heart Class III or IV heart failure, and/or 2) dialysis dependent renal failure. These illnesses were chosen based on successful recruitment during the K99 phase, and the disease criteria were chosen to identify groups of patients with a median survival of about 2 years.

**Nurse Participants.** The nurse participants (N=80) will be the acute care nurse who is caring for the patient.

**Nurse Eligibility criteria.** Nurses will be age 18 or older, able to read English, and able to confirm verbally that they were involved in the care of the enrolled patient.

## C. Study Design and Research Methods.

**Design.** This study will use a mixed methods design. The quantitative data will include the patient-reported outcomes on effects of the narrative intervention and will inform potential effect size for the later efficacy trial. The qualitative data will include: 1) patient and nurse exit interviews for triangulation of the quantitative findings and 2) patient’s illness narratives. At this phase of biobehavioral interventional development, both the quantitative and qualitative data give necessary information about acceptability, feasibility, usability for optimization of the narrative intervention.

### Expected Outcomes

The expected outcomes of the R00 phase will be to conduct and complete preliminary testing of the narrative intervention (Phase II). This study will test the effects on QOC and patient reported outcome data and this study will continue to collect data on acceptability from the key stakeholders for evaluation of barriers and facilitators.

**Table 2. Timeline for the R00: Narrative Intervention Study (Phase II ORBIT Model: Proof of Concept Study)**

	YEAR 1	YEAR 2	YEAR 3
Obtain IRB approval			
Review/finalize procedures			

Recruit and randomize pts				
Collect baseline data				
Conduct intervention				
Data analysis: Quantitative				
Data analysis: Qualitative				
Dissemination				
Prepare R01 Submission				

**Recruitment.**

[figure not shown]
*Patient recruitment.* Recruitment rounds will be completed on three units at the University of Colorado Hospital: cardiac progressive care, cardiac-medical, and dialysis. A research team member will round at least weekly to meet with the charge nurses for identification of potential patients. At the hospital, charge nurses will identify potential participants based on eligibility criteria. If any patients are identified, the research team member will deliver a flyer regarding the study to potential patients and describe study protocols and obtain verbal agreement taking precautions to notify the potential participant that participation in the study is totally voluntary and will not affect care. If a patient volunteers at that time, or at later time by notifying a nursing care team member, the research team member will then arrange a convenient time to meet with potential patients to obtain HIPAA and informed consent. At these initial meetings with the potential participant, the PI will complete the official screening, describe the study, review the informed consent, and discuss risks/benefits with the participant.

If a potential patient is identified, then a research team member will introduce the study to the patient by reviewing the patient recruitment flyer and the informed consent. When a patient agrees to enroll, the informed consent will be completed with the patient, and the patient’s baseline measures will be collected. Each patient will receive \$25 after completing the baseline measures and \$25 at completion of data collection.

*Nurse recruitment.* After a patient is enrolled, the research team will collect from the EHR the names of the nurses who cared for the enrolled patients. These nurses will be approached for consent to participate in the study, with the goal of 80 participating nurses for collection of exit interviews. For the nurses who patients were randomized to the intervention, additionally, these 40 nurses will complete the user-centered testing which consists of nurse participant completion of the system usability scale questionnaire and providing any feedback to PI on ease of use, relevance and appeal, efficiency and subjective satisfaction of the nurse’s use of the patient’s story. Nurses will be contacted via e-mail or in-person with a recruitment flyer. After receiving verbal consent for participation via e-mail or in-person, a convenient in-person time will be coordinated for obtaining consent and subsequent data collection for the exit interviews and/or user centered testing. Each nurse will receive \$25 after completing the exit interview.

Weekly follow-up e-mails x 3 times will be sent if there are difficulties recruiting the 80 nurses for exit interviews or the 40 nurses for user-centered testing. If after these three e-mails, the nurse does not enroll, then the research team will attempt to recruit another nurse who attended the patient. Patient participants will not be withdrawn from the study even if a patient participant’s nurse is not enrolled.

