**Randomization.** Randomization to the narrative intervention or usual care will occur at the patient level. The random allocation sequence will be computer generated using random block sizes, an allocation ratio of 1:1, and stratification by illness group. The project statistician will generate the allocation sequence using SAS software and the allocation sequence will be uploaded for study use into REDCap. Upon study completion, baseline characteristics between intervention and control patients will be compared using independent samples t-tests (continuous measures) and chi-square tests (categorical measures). Though balance is assumed, statistical adjustment will be used in outcome analyses in the event of pre-treatment differences between conditions.

**Data collection.** All survey and demographic data will be captured using electronic surveys through REDCap on password-protected iPads/laptops.

**Demographics.** At baseline, age, gender, race/ethnicity, education in years, income level, religion/spirituality preference, and clinical details to identify co-morbidities and severity of illness will be collected for all participating patients. This demographic detail will allow description of outcome means and standard deviations in key patient subgroups, including groups defined by patient race/ethnicity and specific chronic illnesses of heart disease or end-stage renal disease.

**Measures.** For Aim 1, the primary and secondary outcome measures will be collected at three time points from all patient participants. (Table 1). The purpose of these times periods are to collect the outcome measures consistently for usual care and intervention participants. This is based on knowledge gained during the K99 study regarding time to complete the narrative intervention. In the K99 study, for the narrative intervention, on average it took 24 hours post narrative interview to upload the patient's narrative into the EHR.

**Exit Interviews and Usability Scale.** For Aim 2, the patient and nurse exit interviews and system usability surveys from the nurses will be collected approximately 1-week post intervention. (Table 1).

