**Sample Size and Power Analysis.** Sample size estimates were generated to determine power to detect a time by treatment interaction within the proposed repeated measures design. Assuming two-sided alpha = 0.05, a sample size of 80 patients will provide 80% power to detect an effect size associated with treatment effects on changes over time as small as  $f=.14$  (Cohen's  $d = 0.28$ ). This represents a small, clinically relevant effect, but more importantly will provide stable measures of outcome means and standard deviations over time for use in the planned R01 efficacy trial. Modern missing data techniques will be used if patients drop out before all follow-up data is obtained. To minimize concerns for attrition, the time between baseline and follow-up data collection is small. Nonetheless, if patients are lost to follow-up, even if a high level of attrition (e.g., 20%) will allow for the detection of a small effect size of  $f=.16$ .

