### **E. Potential Problems and Alternative Strategies**

**Patient burden.** Thinking and conversing about end-of-life preferences and overall QoL may initially distress some patients and families. Some patients may decide not to participate because these issues are too difficult to deal with in the context of their illness. Further, there is a plan in place for referral to appropriate follow-up services as needed. During the K99 phase, no participants required referrals, and no participants reported feeling that the intervention was too burdensome

**Nonresponse bias and recruitment and attrition.** Patients who participate may differ from those who decline. Data on response rates will be collected and non-respondent characteristics will be examined to estimate the magnitude of any potential nonresponse bias. To decrease concerns about attrition, the study design calls for only a one-week period from enrollment to follow-up data collection. In addition, as described above, we will use an intention-to-treat analysis and modern missing data approaches. During the K99, all enrolled patient participants completed data collection, and only 2 nurse participants were recruitment failures. One nurse participant unenrolled because of a personal family emergency. The other nurse, an outside temporary agency RN, was unable to be contacted. If we cannot recruit a nurse, the patient's data will still be included in outcome and process analyses, which will inform study procedures in the larger trial.

**Blinding and contamination of intervention effects.** Although the R00 study will use computer-randomized assignment to the intervention and usual care groups, given the patient-centered intervention and patient-reported outcomes, it will not be feasible to blind participants (patients or nurses). Future studies could have an active control and blinded outcome assessment to help address this limitation. In the proposed R00 study, it is possible that the nurses may naturally demonstrate improved communication based on their knowledge of the study. To address this possible contamination, future studies could use a cluster randomized design with clinics or healthcare institutions, rather than patients, as the unit of randomization.

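### Nothing holds the individual approach to nurses until the patient's Quality of Communication (QOC) ratings are complete, so usual-care nurses may be primed before they are rated

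*Combined protocol and SAP*

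**What the plan says.** Section IV.A defines the primary outcome, the QOC, as the patient's view of communication with nurses. It does not tie the rating to one named nurse.

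Section IV.C, Nurse recruitment, makes patient enrolment the starting point: "After a patient is enrolled, the research team will collect from the EHR the names of the nurses who cared for the enrolled patients". They are then approached for consent by e-mail or in person, with a flyer. The target is 80 nurses across both arms, and the 40 in the intervention arm also do usability testing. No earliest or latest time for the approach is given relative to any patient survey.

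Table 1 places Time 2 at 24-48 hours after baseline or narrative upload, and Time 3 a further 24-48 hours later. Nurse data come afterwards. Section IV.C (Exit Interviews and Usability Scale) says that "the patient and nurse exit interviews and system usability surveys from the nurses will be collected approximately 1-week post intervention", and Section F (Aim 2, Barriers and facilitators) gives 5-7 days after upload.

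Section IV.E (Blinding and contamination) states that nurses cannot be blinded and that "it is possible that the nurses may naturally demonstrate improved communication based on their knowledge of the study". Its remedy is for later work: "future studies could use a cluster randomized design with clinics or healthcare institutions". It says nothing about when nurses are approached in this trial.

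**The concern.** The nurse's behaviour is what the primary outcome measures. An individual approach can tell a nurse more than general awareness on the unit does. Eligibility requires the nurse to confirm involvement in the enrolled patient's care (Section IV.B), and the nurse consent form covers randomization and the intervention (Section IV.D, Recruitment and Informed Consent). If this happens in usual care before the follow-up ratings, the control scores may no longer reflect usual care.

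Two products of the trial are at stake: the effect size it is to supply for the efficacy trial (Section IV.C, Design), and the outcome means and standard deviations it is to supply for the same purpose (Sample Size and Power Analysis). The second is affected even if the group difference is not.

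**Working it through.** **1. Is there room to wait?** The timings come from Table 1 and Section F.

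- Usual care: Time 2 is at 24-48 h and Time 3 is 24-48 h later, so Time 3 falls at 48-96 h after baseline. If the nurse interview is at about 7 days (168 h, counted from baseline as an assumption because this arm has no upload), the gap after the latest Time 3 is 168 - 96 = 72 h.
- Intervention, with Time 2 counted from upload as in Table 1: the latest Time 3 is 96 h after upload. The earliest nurse interview is 5 days, or 120 h. The gap is 120 - 96 = 24 h.
- Intervention, by Section IV.D (Time 2 right after upload, last survey 24-48 h after upload): the gap is 120 - 48 = 72 h.

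On the nominal schedule, contact can wait until the last survey in both arms and still precede the nurse interview.

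**2. What would priming do to the contrast?** Let D be the true group difference. Let a be the mean rise in QOC from recruitment priming in usual care, and b the rise in the intervention arm.

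Observed difference = D - (a - b). Proportional loss = (a - b)/D.

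- If a = b, the loss is zero.
- If a > b, the contrast is diluted. This is plausible because intervention nurses already receive an alert and the narrative, so a recruitment cue may add little there. That is an inference, and the documents give neither a nor b.
- In both cases the usual-care mean rises by a.

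**3. The plan's power figure.** The Sample Size paragraph says: "Assuming two-sided alpha = 0.05, a sample size of 80 patients will provide 80% power", for f = .14 on the time-by-treatment interaction. No within-patient correlation is given. I assume rho = 0.5 and sphericity, with k = 2 groups and m = 3 times:

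- lambda = f² × N × m/(1 - rho), df1 = (k - 1)(m - 1), df2 = (N - k)(m - 1).
- N = 80, f = .14: lambda = 0.0196 × 80 × 3/0.5 = 9.41, df = 2 and 156, power 78.2%.
- N = 64 (20% attrition), f = .16: lambda = 0.0256 × 64 × 3/0.5 = 9.83, df = 2 and 124, power 79.8%.

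Both agree with the stated 80% to within rounding of f. The result depends on rho: the f detectable with 80% power at N = 80 is .169 for rho 0.3, .143 for 0.5 and .091 for 0.8. The calculation contains no allowance for contamination.

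**4. Illustration of dilution.** The percentages in the first column are assumed. The rest follows from the formula in step 3 with rho = 0.5.

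| Assumed loss | f | Power at N = 80 | Total N for 80% power |
|---|---|---|---|
| 0% | .140 | 78.2% | 84 |
| 10% | .126 | 68.6% | 104 |
| 20% | .112 | 57.7% | 130 |
| 30% | .098 | 46.2% | 170 |
| 50% | .070 | 25.5% | 330 |

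The first row needs 84 rather than 80 because f is rounded to .14.

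**5. Is the last rating defined in both arms?** Table 1, Section IV.C (Measures) and Section IV.D (Quantitative Data) give every patient three assessments. The usual-care paragraph of Section IV.D gives baseline and a single follow-up at 24-48 hours. A rule tied to Time 3 may therefore have no referent in usual care until these places are reconciled.

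**The case against.** The strongest reply is that the plan does not schedule an early approach. Enrolment governs the collection of names, while the approach itself is undated. The text speaks of nurses who have already cared for the patient, and it links consent to interviews that come after the last rating. A reader might infer that nurses are contacted before Time 2 and Time 3 by design; the documents do not say so. What stands is that nothing prevents it. Up to three weekly reminder e-mails may be sent before a replacement nurse is sought, which gives a team aiming for an interview at about a week a reason to start early. The same reminders mean that some approaches will fall after Time 3.

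The second reply is that both arms are approached in the same way, so priming may cancel. That is correct if priming is equal and additive. A reader might infer certain shrinkage toward zero, but this needs the further assumption that the cue adds more in usual care.

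Third, the QOC concerns nurses in general, one nurse is sought per patient, and some recruitment will fail. A reader might infer that all 40 usual-care patients are exposed; the documents do not support that.

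Fourth, contamination is already disclosed and the study is preliminary. Disclosure stands as an honest limitation, but it does not address a sequence that this trial controls.

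Finally, a later approach leaves other routes open: flyers to nursing staff, charge nurses who identify candidates, and patients who may tell their nurses. This stands, and the fix removes only one route.

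**Conclusion.** The concern holds as an avoidable, uncontrolled route to bias in the primary outcome, not as a demonstrated bias. The plan allows nurses in both arms to be approached individually at any time after patient enrolment, and it accepts that knowledge of the study may change communication. Usual-care QOC scores could rise. The contrast could be diluted if priming adds more in usual care than in the intervention arm.

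The size is unknown. The power figures for 10% to 50% dilution show sensitivity only; they rest on assumed losses, a correlation of 0.5 and sphericity. A reader might want a single expected loss, for example 5% to 30%, from taking half to all usual-care ratings as primed and priming as worth 10% to 30% of the intervention effect (0.5 × 0.1 = 5%; 1 × 0.3 = 30%). Those inputs have no source in the documents, and the product also assumes no priming in the intervention arm, so it should not be quoted as an estimate.

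The change is worth making because it is cheap and the nominal schedule has room for it.

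**What to change.** In Section IV.C, Nurse recruitment:

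- State that nurse names may be collected from enrolment. No nurse in either arm is individually approached, e-mailed or given the nurse flyer about a specific patient until that patient's last scheduled QOC survey is complete or its window has closed.
- Leave the EHR alert to intervention nurses unchanged, since it is part of the intervention.
- Record the date of each nurse approach, so that the order of approach and rating can be checked.
- Do not use a general unit-level nurse consent as a workaround. Randomization is by patient, so it would widen awareness among nurses who may care for both arms.

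Reconcile the usual-care paragraph of Section IV.D with Table 1, Section IV.C (Measures) and Section IV.D (Quantitative Data), so that the last QOC survey is defined in both arms.

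Cost: a short addition to the recruitment text, one recorded date per approach, and the schedule reconciliation. Nurse recruitment starts a few days later, so a few nurses may be harder to reach; in the K99 study one agency nurse could not be contacted. Any field observation of nurses that needs earlier consent in the intervention arm should be written in as a stated exception. Unit-level awareness from flyers, charge nurses and patients themselves remains and should stay listed as a limitation.
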